### **ABBREVIATIONS**

Abbreviation	Definition
AAR	Annualized attack rate
ADA	Antidrug antibody
ADaM	Analysis Data Model
AE	Adverse event
AECI	Adverse event of clinical interest
AIP	Acute intermittent porphyria
ALA	Delta-aminolevulinic acid
ALAS1	5-aminolevulinic acid synthase 1
ATC	Anatomic Therapeutic Class
BMI	Body mass index
BPI-SF	Brief Pain Inventory - Short Form
CDISC	Clinical Data Interchange Standards Consortium
cERD	Circulating extracellular RNA detection assay
CI	Confidence interval
CSR	Clinical study report
CTCAE	Common Terminology Criteria for Adverse Events
CYP	Cytochrome P450
DILI	Drug Induced Liver Injury
ECG	Electrocardiogram
eCRF	Electronic case report form
eDISH	Evaluation of drug-induced serious hepatotoxicity
eGFR	Estimated Glomerular Filtration Rate
EQ-5D	EQ-5D Quality of Life questionnaire
EOS	End of Study
GalNac	N-acetyl glactosamine
HLT	High level term
ISR	Injection site reaction
LFT	Liver function test
LLOQ	Lower Limit of Quantification
mBMI	Modified body mass index
MedDRA	Medical Dictionary for Regulatory Activities
mRNA	Messenger ribonucleic acid
ms	Millisecond
NCA	Non-compartmental analysis
PBG	Porphobilinogen

Abbreviation	Definition
PD	Pharmacodynamic(s)
PK	Pharmacokinetic(s)
PT	Preferred term
Q1	First quartile
Q3	Third quartile
QOL	Quality of life
QTc	Corrected QT interval
QTcB	QTc using Bazett's formula
QTcF	QTc using Fridericia's formula
SAE	Serious adverse event
SAP	Statistical Analysis Plan
SD	Standard deviation
SEM	Standard error of the mean
SI	Standard International (unit)
SMQ	Standardized MedDRA Query
SOC	System organ class
SRC	Safety Review Committee
ULN	Upper limit of normal
WHO	World Health Organization

#### 1. INTRODUCTION

This Statistical Analysis Plan (SAP) has been written based upon clinical protocol (amendment 4.0, date: 02 August 2017) and outlines the planned analyses for safety, Pharmacodynamic (PD), clinical activity and Pharmacokinetic (PK) in patients with acute intermittent porphyria (AIP).

This SAP supersedes the statistical considerations described in the clinical protocol (amendment 4.0; date: 02 August 2017). If there are differences between the statistical considerations in this SAP compared to the protocol, then this will be identified in the clinical study report (CSR).

The purpose of this SAP is to summarize key analyses to be conducted for each objective and presented in the CSR. Population PK or PK-PD analysis is out of scope and will be described in another document. Tables, Listings, and Figures mock shells will also reside in a separate document.

#### 2. STUDY DESIGN

Study ALN-AS1-002 is an open-label, extension study designed to evaluate the long-term safety, clinical activity of givosiran in patients with AIP. The number of patients included up to 16 patients from Part C in the parent study ALN-AS1-001.

Eligible patients who completed Part C in the parent study either received the same dosing regimen as the pivotal Phase 3 study (e.g. 2.5 mg/kg every month) or had 1 or more dosing regimen changes across studies. The change in dosing regimen for a patient may occur due to emerging data and decisions from the Safety Review Committee (SRC). After a patient has completed 12 months of givosiran administration in this study (6 months in an every month dosing regimen), and where applicable country and local regulations and infrastructure allow, study procedures, including givosiran administration may take place at the patient's home by a healthcare professional. The expected duration of treatment for each patient is up to 36 months (3 years) followed by a post-treatment visits at either month 39/Early Termination visit or month 42.

### 3. OBJECTIVES OF THE STUDY

# 3.1. Primary Objective:

• Evaluate the long-term safety and tolerability of givosiran in patients with AIP

# 3.2. Secondary Objectives:

- Assess the PD effect of ALN-AS1 over time
- Assess the clinical activity of ALN-AS1 over time

# 3.3. Exploratory Objectives:

- Characterize the PK profile of ALN-AS1
- Assess changes in health-related quality of life (QOL)
- Characterize analytes related to targeting the heme biosynthesis pathway

# 4. **POPULATIONS**

Population	Definitions
Safety Analysis Set	All patients who receive any amount of study drug
PD Analysis Set	All patients who receive any amount of study drug and who have at least 1 post-dose blood sample for PD
PK Analysis Set	All patients who receive any amount of study drug and have at least 1 post-dose blood sample for PK and who have evaluable PK data

Safety Analysis Set will be used to analyze safety and clinical activity data. The PK and PD Analysis Sets will be used to conduct PK and PD analyses, respectively.

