#### 6. STATISTICAL METHODOLOGY

#### **6.1.** General Considerations:

As this is an extension study, formal statistical analyses will not be performed. All summaries will be descriptive.

Data will be presented in by-patient data listings. The listings will contain study days as described below:

Study day: relative to the first dose of givosiran in this study. The first dose date is designated as Day 1. On treatment study days will be calculated as: evaluation date – first dose date+1. Pre-treatment study days will be calculated as: evaluation date – first dose date.

Continuous variables will be summarized using the following descriptive summary statistics: number of patients (n), mean, standard deviation (SD), median, quartiles (first quartile [Q1], third quartile [Q3]), minimum value, maximum value, and when specified, standard error of the mean (SEM). The precision of the measurement for each continuous variable will be used to determine the number of decimal places to present in tables, figures and derived listings. Minimum and maximum values will be reported with the same precision as the units of measure. The mean, median, SD, quartiles, and SEM will be reported to 1 greater decimal place. Any values that require transformation to standard units (metric or Standard International [SI]) will be converted with the appropriate corresponding precision.

Frequencies and percentages will be presented for categorical and ordinal variables. If there are missing values, the number of missing values will be presented, but without a percentage. Percentages will be based on the number of non-missing values.

For assessments with repeated collection at a given study visit (e.g. electrocardiogram [ECG] parameters), the mean will represent the value at that visit unless otherwise noted.

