#### 6.5. Visit Windows

Data will be tabulated and analyzed per the visit as recorded in the electronic case report form (eCRF).

Data collected at unscheduled visits will be included in by-subject listings and figures, but no assignment to a scheduled visit will be made for the purposes of by-visit summary tabulations. However, unscheduled visits will be considered for any categorical shifts summaries (e.g. shifts from baseline to 'worst' post-baseline value).

For patients who discontinued treatment, the time window for AEs, PD (ALA/PBG/ALAS1), attack and hemin use will be up to 28 days from the last dose.

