#### 7. STATISTICAL METHODOLOGY

### 7.1. Patient Disposition

Patient disposition will be summarized and include the total number and percentage of patients in the following categories:

- Enrolled Patients (signed informed consent and met eligibility)
- Treated Patients
- Completed Patients
- Safety Analysis Set
- PD Analysis Set
- PK Analysis Set

Summaries of the number and percentage who discontinued study treatment based upon primary reason for discontinuation (e.g. AE, Death, Lost to Follow-up, Physician Decision, etc.) will be presented. Summaries of the number and percentage who withdrew from study prematurely based upon primary reason for withdrawal (e.g. AE, Death, Lost to Follow-up, Physician Decision, etc.) will also be presented. Per patient data listings will be presented displaying the primary reason the patient discontinued treatment and/or went off study.

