### 7.5. Secondary Analyses

#### 7.5.1. Pharmacodynamic Biomarkers

One of the key secondary objectives is to evaluate the long-term PD effect of ALN-AS1 on urine levels of ALA and PBG.

**ALA and PBG:** Analysis of ALA and PBG concentrations will be performed on the PD Analysis Set. Values will be based upon urine concentrations collected from the central laboratory. In all analyses of urine ALA and PBG, the concentrations will be expressed as mmol/mol of urine creatinine (e.g, creatinine normalized values). Any values recorded as <LLOQ will be assigned a value of LLOQ/2.

Data will be summarized descriptively (n, mean, SD, SEM, median, quartiles, minimum, and maximum) at baseline and each post-baseline scheduled visits. The analysis will be performed separately for scheduled assessments collected not during attacks and all scheduled timepoints. Tabular summaries of actual value, change from baseline and knockdown values (knockdown=-1\*percentage change) will be generated at each scheduled visit. Plots of the group means (±SEM) of actual values and knockdown values will also be generated. Per-patient plots of actual values over time will be generated.

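### The PD Analysis Set requires a post-dose blood sample, but all three named secondary PD measures analysed on it are urine measures

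*SAP*

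**What the plan says.** Section 4 of the SAP defines the PD Analysis Set as "All patients who receive any amount of study drug and who have at least 1 post-dose blood sample for PD" and assigns PD analyses to it. Safety and clinical activity are handled separately: "Safety Analysis Set will be used to analyze safety and clinical activity data".

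Section 6.5 identifies the PD measures when it sets the post-discontinuation window: "the time window for AEs, PD (ALA/PBG/ALAS1), attack and hemin use will be up to 28 days from the last dose".

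Section 7.5.1 opens with the objective: "One of the key secondary objectives is to evaluate the long-term PD effect of ALN-AS1 on urine levels of ALA and PBG". It then fixes the population ("Analysis of ALA and PBG concentrations will be performed on the PD Analysis Set") and the specimen ("Values will be based upon urine concentrations collected from the central laboratory"), with values normalised to urine creatinine.

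Section 7.6.3 places ALAS1 mRNA on the same set, with separate serum and urine analyses. A parenthesis there makes urine ALAS1 part of the secondary PD analysis and serum ALAS1 exploratory.

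Section 7.1 reports the number of patients in the "PD Analysis Set" as a disposition category.

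The two other SAP versions in the file carry the same section 4 definition. This is one error carried forward, not three.

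**The concern.** Entry to the set depends on a specimen in which none of the secondary PD measures is taken. A patient could have a full series of post-dose urine ALA and PBG values and still fail the definition for want of a PD blood sample. The programmer deriving the population flag would then either leave out valid data on a key secondary objective or depart from the written definition with nothing in the SAP to support it.

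The outputs at stake are the ALA, PBG and ALAS1 summaries and group-mean plots, and the PD set count in the disposition table.

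**Working it through.** The SAP gives no figure to reproduce here. The check compares the entry criterion with the specimen, population and status of each named PD measure.

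| PD measure | Specimen | Status | Analysed on | SAP section |
|---|---|---|---|---|
| ALA | Urine | Secondary | PD Analysis Set | 7.5.1 |
| PBG | Urine | Secondary | PD Analysis Set | 7.5.1 |
| ALAS1 mRNA, urine | Urine | Secondary (by the parenthesis) | PD Analysis Set | 7.6.3 |
| ALAS1 mRNA, serum | Blood | Exploratory | PD Analysis Set | 7.6.3 |

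**Counts**
- Secondary measures taken in urine: 3 of 3.
- Secondary measures taken in blood: 0 of 3.
- Blood measures among all named PD measures: 1 of 4, and that one is exploratory.

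**The definition applied literally to a treated patient**

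| Post-dose PD blood | Post-dose PD urine | In the set as written? | Has post-dose secondary PD data? |
|---|---|---|---|
| Yes | Yes | Yes | Yes |
| No | Yes | **No** | **Yes** |
| Yes | No | Yes | No |
| No | No | No | No |

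The second row is the error: the patient has the data the analysis needs and is excluded. The third row is the reverse case: the patient is counted in the set but contributes no post-dose secondary PD value.

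**Is there a cure elsewhere in the SAP?** None was found. Sections 7.5.1 and 7.6.3 refer to the PD Analysis Set without qualifying it, and section 6.5 does not address membership. Section 7.6.3 introduces ALAS1 as a serum and/or urine measure, so the text does not guarantee that every patient gives serum.

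**Scale.** The number of patients in the second row cannot be derived from the SAP. It is zero if every treated patient with post-dose urine also gave at least one post-dose PD blood sample. Section 2 puts the study at up to 16 patients, so each patient is at least 1/16 = 6.25% of the study. That shows only what one patient weighs. It does not estimate how many are affected.

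**The case against.** **Urine ALAS1 is classified inconsistently.** It sits under an exploratory heading, and the opening sentence of section 7.6.3 calls urinary ALAS1 an exploratory biomarker. Only the later parenthesis makes it secondary. The parenthesis is the more specific statement, so a count of three is sound. If urine ALAS1 were set aside, the mismatch would still hold for ALA and PBG, 2 of 2.

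**The blood criterion is not empty and the harm is hypothetical.** Serum ALAS1 is a PD measure analysed on this set, and a single post-dose PD blood sample during up to 36 months of treatment is enough to qualify. Exclusion needs a patient with urine data and no such sample in the whole study. This stands as a limit on the consequence. It does not make the definition right.

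**The protocol might define the set differently.** The protocol is not at hand. However, section 1 of the SAP says that the SAP supersedes the protocol's statistical considerations, so a different definition there would not govern.

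**Little depends on it.** Section 6.1 states: "All summaries will be descriptive". There is no hypothesis test to distort. By-patient listings are not restricted to an analysis set, so an excluded patient's urine values need not vanish from the report. This also stands, and it keeps the point modest.

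**Admitting either specimen leaves the reverse case.** A patient with blood but no post-dose urine would still be in the set. That is true, and a definition per specimen is an acceptable alternative. The n reported for each analyte at each visit already shows who contributes, so the simpler wording is enough.

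**Conclusion.** The concern holds. The membership rule is tied to the wrong specimen for the analyses it governs: 3 of 3 named secondary PD measures are in urine, and the only named blood measure is exploratory. This is a wrong statement in the SAP, not a detail left to the protocol.

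The effect on results is limited and may be nil. The number of affected patients is not given, and no bias or percentage of affected patients is claimed. Only the PD outputs and the PD set count can change. Safety and clinical activity cannot, because they use the Safety Analysis Set.

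The conclusion rests on reading section 4 as written and on taking the parenthesis in section 7.6.3 as settling the status of urine ALAS1. Without the second, it still stands for ALA and PBG. It should be corrected because the definition governs a key secondary objective and the correction costs almost nothing.

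**What to change.** In section 4, change *blood sample* to *urine or blood sample* in the PD Analysis Set row, so that a treated patient qualifies with at least one post-dose PD sample of either kind. Do not add an analyte-specific entry rule: the n at baseline and at each visit shows who contributes, and baseline urine values stay in the summaries.

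The cost is one phrase and one population flag derived from either specimen. The change only widens entry, so no patient now admitted is removed. Sections 7.1, 7.5.1 and 7.6.3 keep referring to the same single set and need no edit.

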#### 5. MISSING DATA

For continuous and categorical variables, data will not be imputed unless otherwise specified.

There will be no imputation used for partial and/or completely missing dates for events defined as 'porphyria attacks' and for dates of hemin medication. For Delta-aminolevulinic acid (ALA)/ Porphobilinogen (PBG) biomarkers, if any value is recorded as <Lower Limit of Quantification (LLOQ) then the assigned value used for calculations will be assigned a value of LLOQ/2.

The following rules will be applied to incomplete dates to determine the reporting of adverse events (AEs) or medications. These imputed dates will not be displayed in listings because these dates are used to determine if the medication was prior or concomitant to first dose in this study and if the AE occurred on or after the first dose in this study. The rules below do not apply to hemin medications or AEs defined as 'porphyria attacks'.

Imputation rules for Start Date of AE:

- If start date is completely missing, then start date will be imputed to be the date of the first dose of study drug
- For a partial start date (day is missing, month is missing or both day and month are missing):
  - partial date < the first dose date: the first day/month
  - partial date = the first dose date: the first dose date
  - partial date > the first dose date: the first day/month

For medications with partial start or stop dates: the first day/month will be imputed for start date, and the last day/month will be imputed for stop date.

For medications with a completely missing start date, the medications will be considered as started prior to the first dose of study drug in this study; medications will be classified as prior or concomitant depending on the medication stop dates. If any medications have a completely missing stop date, then the medication will be assumed as ongoing.

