Summaries of AEs will consist of events which occur or worsen (including date/time when applicable) after the first dose of givosiran in this study. Note: Porphyria attacks are recorded on the AE eCRF, however they will not be reported as AEs but rather as an endpoint of clinical activity (see section 7.5.2); therefore, the term "AE" excludes porphyria events.

An overview of the frequency (percentage) of AEs including the total number of events will be tabulated (summaries such as but not limited to, the number of patients with at least 1 AE, the number of patients with at least 1 AE related to study drug, the number of patients with at least 1 serious AE [SAE], the number of patients who discontinued study drug to an AE). Separate tabulations will be generated by SOC and PT for all AEs, AEs by maximum severity, related AEs, related AEs by maximum severity, SAEs, discontinuation from study drug due to AEs, interruption due to AEs, and deaths. Patient listings will be generated separately for any patient who died, discontinued from study drug and reported any SAEs.

An additional set of AE outputs will also be generated by study groups defined by the initial dose of givosiran [i.e. Patients with an initial dose of 2.5 mg/kg (monthly) in ALN-AS1-002 and Patients with an initial dose of 5 mg/kg (at any time) in ALN-AS1-002].

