### 5. MISSING DATA

For continuous and categorical variables, data will not be imputed unless otherwise specified.

There will be no imputation used for partial and/or completely missing dates for events defined as 'porphyria attacks' and for dates of hemin medication. For ALA/PBG biomarkers, if any value is recorded as <Lower Limit of Quantification (LLOQ) then the assigned value used for calculations will be assigned a value of LLOQ/2.

The following rules will be applied to incomplete dates to determine the reporting of adverse events or medications. These imputed dates will not be displayed in listings because these dates are used to determine if the medication was prior or concomitant to first dose in this study and if the adverse event occurred on or after the first dose in this study. The rules below do not apply to hemin medications or adverse events defined as 'porphyria attacks'.

Imputation rules for Start Date of AE:

- If start date is completely missing, then start date will be imputed to be the date of the first dose of study drug
- For a partial start date (day is missing, month is missing or both day and month are missing):
  - partial date < the first dose date: the last day/month
  - partial date = the first dose date: the first dose date
  - partial date > the first dose date: the first day/month

Imputation rules for End Date of AE:

- If end date is completely missing, then end date remains missing
- For a partial end date (day is missing, or month is missing or both day and month are missing) then the last day/month will be imputed.

If the imputed AE start date is after the imputed AE end date, then the start date will be set to the imputed AE end date.

For medications with partial start or stop dates: the first day/month will be imputed for start date, and the last day/month will be imputed for stop date.

For medications with a completely missing start date, the medications will be considered as started prior to the first dose of study drug in this study; medications will be classified as prior or concomitant depending on the medication stop dates. If any medications have a completely missing stop date, then the medication will be assumed as ongoing.

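### AEs whose start date is missing, or is partial and matches first dose, are dated to first dose even when their recorded end date is earlier

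*SAP*

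**What the plan says.** The file holds three versions of the SAP. I take the one placed first (signature page VV-CLIN-003053) as current, from its position and document number. Its Section 5 (Missing Data) has two rules that send an incomplete AE start date to first dose:

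- Fully missing start: "If start date is completely missing, then start date will be imputed to be the date of the first dose of study drug".
- Partial start: "partial date = the first dose date: the first dose date".

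Partial starts that fall earlier or later than first dose go to the first day or month of the known period. The same section says the imputed dates serve to determine "if the AE occurred on or after the first dose in this study" and are not shown in listings. It gives no rule for AE end dates and no check that a start precedes its end. The second version in the file (VV-CLIN-002514) has the same rules.

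Section 7.4 (Safety Analyses) then builds the AE tables: "Summaries of AEs will consist of events which occur or worsen (including date/time when applicable) after the first dose of givosiran in this study".

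For medications with no start date, Section 5 does look at the other end of the record: "medications will be classified as prior or concomitant depending on the medication stop dates".

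The third version in the file does have AE end-date rules, including one that moves a late start back to when the event ended: "If the imputed AE start date is after the imputed AE end date, then the start date will be set to the imputed AE end".

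**The concern.** Dating an AE to first dose is a sensible default when nothing places the event in time. When an end date before first dose has been recorded, the timing relative to first dose is already known, and the rule overrides it. The result is an analysis record whose start is later than its end, and an event that had resolved before treatment in this study appears in the AE tables. Those tables serve the primary objective.

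The fault would also be hard to see. A listing would show an incomplete start and an end before first dose, while the table counts the event as on treatment. The imputed date that explains the difference is not displayed.

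**Working it through.** The plan states no figure here, so there is nothing to reproduce. The check is to apply the rules to test records and then size the effect.

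**Inputs.** The Section 5 rules of the current version are as quoted. First dose is assumed to be 15 March 2018, for illustration only. An event is classed as on treatment if its imputed start is not before first dose.

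| Case | Recorded start | Recorded end | Imputed start | Class | Start after end? |
|---|---|---|---|---|---|
| a | missing | 20 Feb 2018 | 15 Mar 2018 | on treatment | yes |
| b | Mar 2018 | 10 Mar 2018 | 15 Mar 2018 | on treatment | yes |
| c | 2018 | 20 Feb 2018 | 15 Mar 2018 | on treatment | yes |
| d | Feb 2018 | 20 Feb 2018 | 1 Feb 2018 | before first dose | no |
| e | missing | 2 Apr 2018 | 15 Mar 2018 | on treatment | no |

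Cases a to c fail: each event is known to have ended before first dose. Case d shows that a partial start clearly before first dose is classified correctly. Case e shows the default working as intended.

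**With an end-date check.** If an imputed start later than the end is moved back to the end date, the starts in a, b and c become 20 February, 10 March and 20 February 2018. All three then fall before first dose. Case e keeps 15 March and stays on treatment, so the conservative intent survives.

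**Size.** Section 7.4 counts a patient once per preferred term and also reports the total number of events.

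- Event count: +1 for each misclassified record.
- Patient frequency for the term: 0 if the patient already has that term on treatment. Otherwise it is 100/n percentage points, where n is the number of patients in the column.
- Total column: Section 2 allows up to 16 patients, so with 16 treated the change is 100/16 = 6.25 points. With fewer treated it is larger.
- Group columns (Section 6.4, by parent-study arm and by initial dose): their sizes are not given in the SAP. If 16 patients were split evenly (an assumption), each column would hold 8 and the change would be 100/8 = 12.5 points in the affected column.

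**The case against.** **Section 7.4 offers a way out.** It limits the summaries to events that occur or worsen after first dose, and an event that ended earlier can do neither. A careful programmer could exclude it on that basis. This shows two provisions in tension, but it does not cure the fault, because Section 5 makes the imputed date the test of whether the event falls before or after first dose.

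**The medication contrast proves little.** Whether a drug is concomitant depends by definition on whether it was still being taken at first dose, so its stop date is intrinsic to that question. This stands. The contrast shows that the section can use an end date, not that it contradicts itself.

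**The third version is only background.** Its order is inferred, and a difference from superseded text is not an error. This also stands. The point rests on Section 5 of the current version alone. The third version only shows that a workable check has already been written.

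**The error is conservative and the study descriptive.** Both are true and keep the point minor.

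Three stronger readings are tempting and not supported:

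- A reader might infer that any one misclassified event moves a preferred-term frequency by at least 6.25 points. It does not, because patients count once per term and the change can be 0.
- A reader might infer that events carried over from the parent study trigger the fault. An event still ongoing at first dose has no end date before it and cannot produce the conflict.
- A reader might infer that AE start-date imputation is wrong in general. Only the two kinds of start date quoted are affected.

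**Conclusion.** The point holds as a minor fault in a stated rule. When an AE start is fully missing, or partial and matching first dose at the known precision, Section 5 dates it to first dose regardless of a recorded earlier end. Read as written, an event known to have resolved before first dose becomes on treatment, with a start after its end.

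Few records are likely, since each needs both an incomplete start of this kind and a known end before first dose. How many such records can exist depends on the AE collection window and on how parent-study events are carried into this study's data, which the SAP does not state. The direction is over-counting. The 6.25-point figure assumes that 16 patients are treated and that the patient has no other on-treatment event of that term.

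**What to change.** Amend Section 5 of the SAP to say:

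1. An AE start that is fully missing, or partial and matching first dose, is imputed to first dose only if the AE end date is missing, ongoing, or not before first dose.
2. If the end date is before first dose, the AE is classed as pre-treatment. A partial end date is taken as its latest possible day for this purpose.
3. An imputed start may never be later than the end date.

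Item 2 needs a short AE end-date rule, which the current section lacks. The third version in the file already contains suitable rules that could be restored. The cost is that text and one programming check. Events whose end is unknown, ongoing or not before first dose stay on treatment, so the conservative default is kept.
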